8 SAFETY REPORTING

8.1 Definitions

8.1.1 Adverse Event

Any untoward medical occurrence in a patient or clinical trial patient administered a medicinal product and which does not necessarily have a causal relationship with this treatment.

An AE can therefore be any unfavourable and unintended sign (including an abnormal laboratory finding), symptom or disease temporally associated with the use of the study medication, whether or not considered related to the study medication.

8.1.2 Adverse Drug Reaction (ADR)

All untoward and unintended responses to an investigational medicinal product related to any dose administered. All cases judged by either the reporting medically qualified professional or the Sponsor as having a reasonable suspected causal relationship to the study medication qualify as ADRs.

8.1.3 Unexpected Adverse Reaction

An adverse reaction, the nature or severity of which is not consistent with the applicable product information (e.g. IB for an unauthorized investigational medicinal product or summary of product characteristics for an authorized product).

8.1.4 Serious Adverse Event or Serious Adverse Reaction

Any untoward medical occurrence or effect at any dose that:

- Results in death,
- Is life-threatening,
- Requires inpatient hospitalization or prolongation of existing hospitalization,
- Results in persistent or significant disability/incapacity, or
- Is a congenital abnormality / birth defect.

NOTE: Other events that may not result in death, are not life threatening, or do not require hospitalization, may be considered a serious adverse event when, based upon appropriate medical judgment, the event may jeopardize the patient and may require medical or surgical intervention to prevent one of the outcomes listed above. Examples of such events include, but are not limited to, severe early onset reaction such as anaphylaxis, vasovagal episodes, episodes of hypotonia, hyporeactivity or hyperventilation, or convulsions.

All SAEs will be reported to the Sponsor (or designee) within 24 hours of notice of occurrence. The Sponsor (or their designee) will be responsible for reporting the AE to the appropriate regulatory authorities and the ECs within the legally specified period. It is important to distinguish between SAEs and severe AEs. Severity is a measure of intensity whereas seriousness is defined by the criteria above. An AE of severe intensity need not necessarily be considered serious. For example, a migraine headache that incapacitates a patient for many hours may be considered a severe AE, whereas a stroke that results in a limited degree of disability may be considered mild, but should be reported as an SAE.

8.1.5 Suspected Unexpected Serious Adverse Reaction (SUSAR)

A serious adverse reaction, the nature or severity of which is not consistent with the applicable product information (e.g. IB for an unapproved investigational product or Summary of Product Characteristics for an approved product).

Treatment Emergent Adverse Events (TEAEs)

Treatment emergent adverse events (TEAEs) are undesirable events not present prior to medical treatment, or an already present event that worsens either in intensity or frequency following the treatment.

8.2 Procedures for Recording of Safety Events

8.2.1 General

All adverse events occurring during the Study (from the time point of signing of the ICF until completion of patient's study participation or premature withdrawal) observed by the

investigator or reported by the patient, whether or not attributed to the IMP, shall be recorded in patient's medical records and on the eCRF.

The following information shall be recorded:

- Description
- Date of onset and end date
- Severity
- Assessment of relatedness to the IMP
- Seriousness
- Measures taken for management of the AE
- Outcome of the event

Follow-up information should be provided as necessary.

AEs considered as being related to the IMP as judged by a medically qualified Investigator, or the Sponsor, must be followed until their resolution or when patient's status is considered as stable. All related AEs that result in a patient's withdrawal from the Study or are present at the end of the Study, should be re-evaluated and if needed followed until a satisfactory resolution occurs.

It will be left to the investigator's clinical judgment whether or not an AE is of sufficient severity to require termination of IMP administration. A patient may also voluntarily withdraw from IMP administration due to AEs perceived as intolerable. If either of these occurs, the patient will be given appropriate care under medical supervision until symptoms cease or the condition becomes stable.

The severity of reported events shall be assessed on the following scale:

- 1 = mild
- 2 = moderate
- 3 =severe

The causal relationship of AEs to the IMP must be assessed by the investigator, or by a medically qualified designee, in accordance with the following criteria:

| TERM | DEFINITION |
|------------------|---|
| Unrelated | Clinical event with an incompatible time relationship to administration of the investigational medical product (IMP), and that could be explained by underlying disease or other drugs or chemicals or is incontrovertibly not related to the IMP |
| Possibly related | Clinical event with a reasonable time relationship to IMP administration, and that is unlikely to be attributed to concurrent disease or other drugs or chemicals |
| Related | Clinical event with plausible time relationship to IMP administration and that cannot be explained by concurrent disease or other drugs or chemicals |

The degree of certainty with which an AE is attributed to IMP administration (or alternative causes, e.g. natural history of the underlying disease, concomitant therapy, etc.) will be determined by how well the experience can be understood in terms of one or more of the following:

- Known pharmacology of the IMP
- Reactions of a similar nature have been previously observed with the IMP or this class of drug
- A temporal relationship to IMP administration, terminating with IMP withdrawal or recurring on re challenge
- Alternative cause

At the last scheduled visit, the investigator shall instruct each patient to report any subsequent event(s) that the patient, or her personal physician, believes might reasonably be related to participation in this Study. The investigator should notify the Sponsor (or designee) of any death or SAE occurring at any time after a patient has discontinued or terminated study participation that may reasonably be related to this Study.

8.2.2 **Pre-existing Conditions**

For purposes of this Study a pre-existing condition means a diagnosed, clinically significant finding, symptom or laboratory abnormality present at screening. Subsequently, during the course of the Study it shall be recorded as an AE/SAE if the frequency, intensity, or the character of the condition worsens during the study period.

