Patients should not have used topical ocular steroids for 7 days prior to entry to the trial but, at the discretion of the investigator, may receive them as rescue medication during the trial. A comparison of the number of patients requiring rescue therapy at any stage of the trial and the number on such therapy at the end of the trial will be an additional exploratory endpoint.

Use of systemic immunosuppressives, antihistamines or corticosteroids during the trial is forbidden. Patients who, in the opinion of the investigator, require such treatment will be withdrawn from the trial. If the reason for giving such treatment is related to their primary pathology (AKC, VKC, or severe allergic conjunctivitis (SAC or PAC)) they will be regarded as treatment failures.

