6.4.1 Emergency Unmasking for Safety Reasons

In the unlikely event of an emergency where, in the opinion of the investigator, discontinuation of study treatment for an individual patient is not sufficient and the study treatment must be unmasked in order to evaluate further course of action, the investigator will have direct access to the randomisation codes for unmasking.

The investigator will consult his own copy of the randomisation codes supplied in a sealed envelopes individually numbered for each patient and decide what, if any, further action to take.

Once the study treatment has been unmasked, the subject will complete the Early Termination visit and then discontinue study treatment. The subject will also be seen for post-treatment follow-up.

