7.2 Withdrawal Criteria

In accordance with applicable regulations, a patient has the right to withdraw from the study at any time and for any reason without prejudice to their future medical care by the physician or at the Institution. Should a patient withdraw from the study, the patient will not undergo any further study-specific procedures or receive any treatment mandated by the protocol.

If a patient fails to attend scheduled trial assessments, the Investigator must determine the reasons and the circumstances as completely and accurately as possible.

In the event of the premature withdrawal of a patient from the trial, the end of trial visit should be carried out as completely as possible. Minimally, a safety assessment should be performed.

In the case of withdrawal due to the occurrence of unacceptable toxicity, the patient will be requested to remain under the supervision of the Investigator until the toxicity has resolved or is no longer considered to be clinically significant by the Investigator.

If an AE classified as severe results in patient withdrawal from the study, the patient will be followed until the AE (or SAE) resolves or stabilises, and any interventions required to resolve or stabilise the event will be recorded in the eCRF.

All withdrawals must be documented in the eCRF. A patient may be withdrawn in any of the following circumstances:

- Withdrawal of consent (mandatory withdrawal)
- Intake of non-permitted concomitant medications (may be discussed with the Sponsor and dependent on the nature of the medication)
- Patient is non-compliant with more than three consecutive missed doses and two missed clinic visits, in the opinion of the Investigator (discretionary withdrawal)
- If discontinuation is considered necessary by the Investigator and/or Sponsor (mandatory withdrawal)
- Request of Regulatory Agency (mandatory withdrawal)
- Patient develops an illness that would compromise his participation in the study (may be discussed with sponsor)
- Pregnancy

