11.4 Number of Subjects

Up to 19 patients (3 in part 1 of the study and up to 16 in part 2), to include active and placebo treated, will be enrolled under this protocol. The sample size for this study was determined based on practical, and not statistical, considerations.

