11.5 Significance Level

The primary objective of the study is to assess the safety and tolerability of topical rVA576 for AKC, VKC and severe allergic conjunctivitis (SAC or PAC) and the study is not powered for the primary analysis.

For the secondary efficacy analyses, a nominal level of 5% will be considered significant, and no multiplicity adjustment will be introduced. Some significant findings are expected to occur by chance so undue consideration will not be given to any particular significant difference. Interpretation of the results will be based on patterns of differences and in conjunction with the results of the primary analyses.

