6 ANALYSIS PLAN

6.1 General

Summary statistics for continuous variables will consist of number of non-missing observations (n), mean, standard deviation (SD), minimum, 25th percentile, median, 75th percentile and maximum, unless specified otherwise. The precision of these variables is defined in the table, figure and listing shells document.

For categorical variables the number and percentage of patients in each category will be presented, based on the number of non-missing observations apart from disposition of patients, protocol deviations, background and demographic characteristics, prior and concomitant medications/procedures and adverse events where the percentage will be based on the number of patients in the analysis set.

Any statistical tests will be performed using a two-tailed 5% overall significance level, unless otherwise stated. The null hypothesis at all times will be that the treatments are equivalent. All comparisons between the treatments will be reported with 95% confidence intervals for the difference.

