6.5 Disposition of patients

For Part 1 and Part 2, the number and percentage of all patients enrolled, included in the RAN, FAS, SAF, PK Analysis Set, who completed the study and prematurely discontinued the study, who completed study treatment and prematurely discontinued study treatment and study duration, will be summarised.

The number and percentage of patients will be summarised by their reasons for withdrawal from the study and study treatment.

Study duration will be derived as the number of days between date of starting drug administration and the date of study completion or the date of early study withdrawal. The date of starting drug administration will be determined from the Comfort Diary Card CRF page.

Eligibility for each of the analysis sets along with reasons for exclusion will be listed. Study completion/withdrawal data will be listed.

6.6 **Protocol Deviations**

Details of all protocol deviations (date, deviation category, specific details and classification of major or minor) and patient eligibility will be listed.

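### A patient who leaves early with no ocular TEAE on record counts as a 56-day non-event, so unequal early withdrawal can bias the primary difference

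*Protocol*

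**What the plan says.** **Endpoint.** Protocol 5.2.1 and SAP 2.2 define the primary endpoint as the incidence of ocular TEAEs in the 56 days after randomisation, Part 2 only.

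**Collection.** Protocol 8.2.1 has AEs recorded "from the time point of signing of the ICF until completion of patient's study participation or premature withdrawal". After that point it asks the investigator to notify only deaths and SAEs that may reasonably be related to the study. Protocol 7.2 states: "Should a patient withdraw from the study, the patient will not undergo any further study-specific procedures". The same section asks for an end-of-trial visit on premature withdrawal, with a safety assessment as the minimum. It continues follow-up of unacceptable toxicity, and of a severe AE that led to withdrawal.

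**Routes out.** For systemic immunosuppressives, antihistamines or corticosteroids, protocol 6.3 says: "Patients who, in the opinion of the investigator, require such treatment will be withdrawn from the trial". Protocol 7.2 lists non-permitted medication only as a circumstance in which a patient may be withdrawn, open to discussion with the sponsor. For a patient who is unmasked and then stops treatment, protocol 6.4.1 adds: "The subject will also be seen for post-treatment follow-up".

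**Analysis.** SAP 6.1 exempts several summaries from the non-missing denominator, among them "adverse events where the percentage will be based on the number of patients in the analysis set". SAP 6.3 puts anyone with at least one dose in the Safety Analysis Set, and SAP 6.2 allows no imputation. SAP 6.14.1.1 reports the crude percentage per arm and an exact 95% confidence interval for the difference by the Chan and Zhang method. SAP 6.5 separately counts patients "who completed study treatment and prematurely discontinued study treatment" and those who completed or left the study.

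**The concern.** The endpoint has a fixed 56-day window, but observation ends when a patient leaves, and nothing in the primary analysis allows for the shorter time at risk. The SAP foresees sensitivity or additional analyses for the comfort score (6.10.2.1.2) and the clinical score (6.10.2.3.2), but none for incomplete AE follow-up.

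Safety is the primary objective. If more active-arm than placebo patients leave early for reasons unconnected with their eyes, the active arm's ocular TEAE rate is understated and the drug looks better tolerated than it is. More such losses on placebo would do the reverse. Later composite score, ETDRS and TBUT values are lost for the same patients. Data that were never collected cannot be recovered at the analysis stage.

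**Working it through.** **Plan figures.** There is no powered sample size to reproduce. Protocol 11.4 says: "The sample size for this study was determined based on practical, and not statistical, considerations". Protocol 11.5 adds that "the study is not powered for the primary analysis". The counts are consistent: 3 + 16 = 19 patients, and 16/2 = 8 per arm in Part 2. One patient is 1/8 = 12.5 percentage points.

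**How one patient is counted.** Take a patient dosed on Day 1 who leaves on Day 14 for a non-ocular reason, with no ocular event by the end-of-trial visit.
- Protocol 8.2.1 and 7.2: routine AE recording stops at that point.
- SAP 6.3 and 6.1: the patient stays in the denominator.
- SAP 6.2 and 6.14.1.1: nothing is imputed, and the patient adds 0 to the numerator.

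The result is a 56-day non-event based on 14 days of observation.

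**Expected fall in one arm.** The documents give no ocular TEAE rate or dropout rate, so all inputs here are assumptions: 56-day risk p of 30%, 50% or 70%; constant hazard; k of 8 patients leaving on day t, independently of AEs.

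- Chance of an event by day t: p_t = 1 - (1 - p)^(t/56)
- Expected crude rate: [(8 - k)p + k·p_t]/8
- Fall: k(p - p_t)/8

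Example: for p = 50% and t = 14, p_t = 1 - 0.5^0.25 = 15.9%. With k = 1 the rate is (7 × 0.50 + 0.159)/8 = 45.7%, a fall of 4.3 points.

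| p | t (day) | p_t | Fall, k=1 | k=2 | k=3 |
|---|---|---|---|---|---|
| 30% | 14 | 8.5% | 2.7 | 5.4 | 8.1 |
| 30% | 28 | 16.3% | 1.7 | 3.4 | 5.1 |
| 50% | 14 | 15.9% | 4.3 | 8.5 | 12.8 |
| 50% | 28 | 29.3% | 2.6 | 5.2 | 7.8 |
| 70% | 14 | 26.0% | 5.5 | 11.0 | 16.5 |
| 70% | 28 | 45.2% | 3.1 | 6.2 | 9.3 |

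The range is 1.7 to 16.5 percentage points.

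**Against the planned interval.** Exact 95% intervals of the Chan–Zhang type (score statistic, two one-sided 2.5% tests, grid of 1 point) for 8 versus 8:
- 4/8 v 4/8: difference 0, about -50 to +50 points
- 3/8 v 4/8 (one event missed): -12.5, about -60 to +40
- 2/8 v 4/8 (two events missed): -25, about -67 to +25

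**When withdrawal follows an ocular event.** Keep p = 50% for those who stay, but let every leaver have an ocular TEAE recorded before or at withdrawal. The rate is [(8 - k) × 0.5 + k]/8 = 56.3%, 62.5% or 68.8% for k = 1, 2 or 3. The arm's rate then does not fall.

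**The case against.** A reader might infer that every patient who stops or withdraws is scored as event-free, so that the arm with more early stopping must show a lower rate. The documents do not support this. Ocular TEAEs up to and including the end-of-trial safety assessment count. Protocol 8.2.2 requires worsening of a pre-existing condition to be recorded as an AE. A patient who leaves because the drops are not tolerated, or because the eye disease needs systemic treatment, may therefore already be in the numerator, provided the event is coded under Eye disorders. The last calculation above shows that this can leave the rate higher.

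A reader might also infer that the protocol treats stopping the drops and leaving the study as the same thing. It does so only in part. Protocol 8.2.1 speaks of ending or withdrawing from IMP administration, 6.4.1 gives unmasked patients follow-up, and SAP 6.5 counts the two separately. It is also an inference that the no-further-procedures sentence in 7.2 governs investigator-led stops, because it follows directly on the patient's right to withdraw. What remains is that no section gives a visit and AE-collection path to a patient who only stops the drops. Protocol 8.2.1 promises medical care until the condition settles, not scheduled assessments.

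Two further points are fair. A crude incidence over all treated patients is a conventional safety summary, and unequal follow-up would show up in the study duration and exposure summaries (SAP 6.5 and 6.9.2). The interval is also so wide that sampling error dominates. Neither point removes the problem: visibility does not restore missed events, and a wide interval does not correct a bias.

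**Conclusion.** The concern holds in a limited form. AE recording that ends at premature withdrawal, combined with an all-dosed denominator, turns early leavers with no recorded ocular TEAE into 56-day non-events, and unequal withdrawal can then bias the primary difference. The bias is downward mainly for non-ocular reasons, withdrawn consent and loss to follow-up. Nothing in the documents shows that such withdrawals will differ by arm.

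Under the stated assumptions, one arm's expected rate falls by about 2 to 17 points, in a comparison whose interval runs from roughly -50 to +50. The trial's sample size is unaffected, since it was not statistically derived. Apart from this, protocol 6.3 and 7.2 contradict each other on whether needing or taking prohibited medication leads to withdrawal, and must be reconciled. The point merits correction because the remedy is cheap and the endpoint is primary.

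**What to change.** **Protocol.** In 6.3, 7.2 and 8.2.1, separate stopping the study drops from withdrawing from the study. Patients who stop the drops and still consent keep the already scheduled visits and AE collection to Day 56 and the Day 84 follow-up, identically in both arms. AE collection then ends at Day 84 or at withdrawal of consent. Reconcile 6.3 with 7.2 on prohibited medication. Align the unmasking passage (6.4.1) and the pregnancy passages (4.4, 7.2 and 8.2.4) with this data-collection rule. The change concerns data collection only and leaves untouched when treatment is stopped.

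**SAP.** State in 6.14.1.1 how incomplete 56-day follow-up is handled. Report AE follow-up time per arm within the 56-day window beside the primary result. Add a sensitivity analysis: either time to first ocular TEAE, or a worst-case count in which early leavers with no recorded ocular TEAE are taken as events.

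**Cost.** A short protocol amendment, a few already scheduled visits for the few patients who stop early, and a small amount of analysis work. No new procedure is needed. Patients who withdraw consent will still be lost, so the sensitivity analysis is needed even with the amendment.

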8.2.3 Overdose

The total amount of rVA576 in single drops is so small that overdosage by this route is considered to be impossible (1 drop of rVA576 0.25% solution contains 0.15 mg, one three hundredth of the standard systemic therapeutic dose) even if totally systemically absorbed. Since there are no known adverse events associated with systemic overdosage the risk of ocular overdosage, whether accidental or intentional, is therefore considered to be negligible).

8.2.4 Pregnancy

Recombinant rVA576 is contraindicated during pregnancy. If pregnancy is suspected, a blood sample for serum HCG examination must be sent to the sub-contracted laboratory within 48 hours. As during the first pregnancy weeks the test may be negative it may be confirmed by an ultrasound examination. If at least one of the above-mentioned examinations is positive, administration of the IMP must be stopped and the patient must be immediately withdrawn from the study. All pregnancies (even if suspected) must be reported on the appropriate eCRF page (Pregnancy form) within 24 hours from the moment when the investigator became aware of the pregnancy (or suspected pregnancy). In any case each pregnancy must be followed till its termination (either by birth of a child or abortion) and the eCRF Pregnancy form has to be updated.

